c Intervention Period includes study treatment and Active Follow-up and Survival Follow-up as defined in Section 4.4 (including for Safety Lead-in portion of the study). Day 0/Week 0 is considered the day of the first infusion of MT-401 (which differs from the Day 1 used for allogeneic HSCT). Each infusion and visit must be at least 2 weeks apart. Active Follow-up Period as defined in Section 4.4: occurs after the last dose of MT-401 has been administered until patient relapses/progresses or declines additional study visits. Timing of Follow-up Visits are in relation to the timing of the Day 0 visit. Sponsor will schedule Day 0 timing for all patients in all groups, including Group 1 SoC arm.

d SoC patients do not need to perform visit Weeks 2 or 4, unless clinically indicated. Week 0 visit for SoC patients may occur between days 85-130 post-HSCT, as instructed by Sponsor.

^e Survival follow-up begins after relapse/progression or active follow-up is completed and occurs every 3 months for 3 years, every 6 months for the remainder of the study (which can be phone contact to collect patient survival status [if alive, last date known alive, and if dead, date of death], and collect any additional anticancer therapy post-MT-401 or SoC received during study.

Confidential Page 19 of 74

f Brief physical exam, to include at a minimum, assessments of the Cardiovascular, Respiratory, and Gastrointestinal systems (height and weight will be needed at screening at minimum and any changes recorded if >10%).

g Pregnancy testing is required unless a patient has no possibility of being pregnant (for example post-hysterectomy). Perform as clinically indicated during intervention period for WOCBP. See Section 8.3.5 for details.

^h On day of MT-401 administration, laboratory assessments and/or disease assessments are completed prior to infusion (see Section 8.2.3 for additional details of laboratory assessments to be performed).

¹ Vital signs obtained within 1 hour pre- and post-infusion (window ± 15 min).

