9.3.4.2. Graft-versus-host Disease- and Relapse-free Survival (Groups 1 and 2)

Graft-versus-host disease- and relapse-free survival (GRFS) is defined as the time from randomization (Group 1) or first dose (Group 2) to date of GVHD, relapse, or death, whichever occurs first. GVHD events are defined as any grade 3-4 acute GVHD or chronic GVHD requiring systemic therapy. A patient who has not experienced any of these events will be censored on the date of their last evaluable disease

Confidential Page 54 of 74

assessment. For patients who remain alive and have no recorded post-baseline disease assessment, GRFS will be censored on the date of randomization (Group 1) or first dose (Group 2). Censoring rules for the analysis of GRFS in Group 1 are presented in Table 11.

Table 11. Censoring Scheme for Primary Definition of GRFS

Situation	Date of Event or Censoring	Outcome
GVHD or relapse	Date of first event type	Event
Death without GVHD or relapse	Date of death	Event
No baseline disease assessment	Date of randomization	Censored
No on-study disease assessments and no death	Date of randomization	Censored
No GVHD, no relapse, and no death	Date of last evaluable disease	Censored
	assessment	
New anti-cancer therapy received without relapse	Date of last evaluable disease	Censored
reported prior to or on the same day as disease	assessment on or prior to the date of	
assessment	initiation of subsequent therapy	
Two or more consecutive missed scheduled disease	Date of last evaluable disease	Censored
assessments	assessment prior to the missed disease	
	assessments	

Abbreviations: AML=acute myeloid leukemia; GRFS=graft-versus-host disease relapse-free survival

The statistical methods for analyzing GRFS are identical to those described for RFS.

GRFS will be summarized for Group 1 and Group 2 Subgroup D, respectively.

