6.4.1.2 Primary Efficacy Variables

Phase 2 Adjuvant (Group 1):

- RFS: defined as the time between the date of randomization and the date of first relapse per ELN recommendations or death by any cause, whichever occurs first. Relapse includes either hematologic and/or molecular relapse as defined in [Table 2](#) at any disease assessment. In the event that no relapse or death is documented prior to analysis cutoff or the start of new anti-cancer therapy, RFS will be censored on the date of the last evaluable disease assessment demonstrating no relapse prior to analysis cutoff or the start of new therapy. For patients who remain alive and have no baseline disease assessment or have no post-randomization disease assessment, RFS will be censored on the date of randomization. In addition, if relapse or death occurs after extended time without disease assessments, RFS will be censored on the date of the last evaluable disease assessment prior to the missed disease assessments.

For patients with relapse or death, a variable will be created to flag whether the earlier date of relapse or death occurs after extended time without disease assessments. The extended time is defined as below:

- Time from randomization date to Day 0 visit + 12 weeks + assessment window of 2 weeks, if the latest assessment prior to the event (relapse or death, whichever is earlier) \leq randomization date + 0.5*time from randomization date to Day 0 visit. For patients without Day 0 visit, an artificial Day 0 visit will be derived as randomization date + mean time from randomization date to Day 0 visit date in MT-401 arm, for analysis purpose only.
- 24 weeks + assessment window of 2 weeks, if the latest assessment prior to the event (relapse or death, whichever is earlier) \leq Day 0 visit + 6 weeks & $>$ randomization date + 0.5*time from randomization date to Day 0 visit
- 38 weeks + assessment window of 5 weeks, if the latest assessment prior to the event (relapse or death, whichever is earlier) \leq Day 0 visit + 18 weeks & $>$ Day 0 visit + 6 weeks
- 78 weeks + assessment window of 5 weeks, if the latest assessment prior to the event (relapse or death, whichever is earlier) \leq Day 0 visit + 37 weeks & $>$ Day 0 visit + 18 weeks
- 104 weeks + assessment window of 5 weeks, if the latest assessment prior to the event (relapse or death, whichever is earlier) \leq Day 0 visit + 78 weeks & $>$ Day 0 visit + 37 weeks

Phase 2 Active Disease (Group 2):

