- Graft-versus-host disease RFS (GRFS): defined as the time from randomization to date of GVHD, relapse, or death, whichever occurs first. A GVHD event is defined as any grade

3-4 acute GVHD or chronic GVHD requiring systemic therapy. A patient who has not experienced any of these events prior to analysis cutoff or the start of new anti-cancer therapy, will be censored on the earlier date of their last GVHD assessment and evaluable disease assessment demonstrating no relapse prior to analysis cutoff or start of new therapy. For patients who remain alive and have no baseline disease assessment or have no recorded post-randomization disease assessment, GRFS will be censored on the date of randomization. In addition, if a GVHD event, relapse, or death occurs after extended time without GVHD assessments, GRFS will be censored on the date of the last evaluable GVHD assessment prior to the missed GVHD assessments or on the date of the last GVHD assessment prior to the missed GVHD assessments.

Phase 2 Active Disease (Group 2):

- ORR: defined as the proportion of treated patients who achieve a best response of CR_{MRD}-, CR, CRi, MLFS, or PR using the ELN recommendations and repeated MRD assessment. This endpoint only applies to Group 2 Subgroup C.
- DOR: defined as the time between the date of first documented response of CR_{MRD}-, CR, CRi, MLFS, or PR to the date of the first documented progression per ELN recommendations or death due to any cause, whichever occurs first. For patients who neither progress nor die prior to analysis cutoff or the start of new anti-cancer therapy, DOR will be censored on the date of their last evaluable disease assessment on or after the assessment of first documented CR_{MRD}-, CR, CRi, or PR and prior to analysis cutoff or start of new therapy. This endpoint only applies to Group 2 Subgroup C.
- PFS: defined as the time between the date of first dose and the date of documented progression or death by any cause, whichever occurs first. For patients who remain alive and whose disease has not progressed prior to analysis cutoff or the start of new anti-cancer therapy, PFS will be censored on the date of last evaluable disease assessment prior to analysis cutoff or start of new therapy. For patients who remain alive and have no baseline disease assessment or have no recorded post-dose disease assessment, PFS will be censored on the date of first dose of study medication. This endpoint only applies to Group 2 Subgroup C.

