7.7 Changes in the Conduct of the Study or Planned Analyses

There were no changes to the study conduct or planned analyses identified within the development of this SAP, relative to the descriptions provided within the clinical study protocol.

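### The SAP ties missed-visit censoring in GRFS to GVHD assessments rather than disease assessments, so a relapse or death can count for RFS yet be censored in GRFS, unlike Protocol Table 11

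*SAP*

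**What the plan says.** **SAP 6.4.1.3 (GRFS), events after a gap.** The rule reads "if a GVHD event, relapse, or death occurs after extended time without GVHD assessments, GRFS will be censored on the date of the last" and continues "evaluable GVHD assessment prior to the missed GVHD assessments or on the date of the last GVHD assessment prior to the missed GVHD assessments". Both halves of the alternative name a GVHD assessment.

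**SAP 6.4.1.3 (GRFS), event-free patients.** They "will be censored on the earlier date of their last GVHD assessment and evaluable disease assessment demonstrating no relapse".

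**SAP 6.4.1.2 (RFS).** Here the gap is one in disease assessments: "if relapse or death occurs after extended time without disease assessments, RFS will be censored on the date of the last evaluable disease assessment". The gap limits that follow belong to a variable meant to "flag whether the earlier date of relapse or death occurs after extended time without disease assessments". No counterpart is given for GVHD assessments.

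**Protocol 9.3.4.2 and Table 11 (GRFS).** "A patient who has not experienced any of these events will be censored on the date of their last evaluable disease" assessment. Table 11 censors after two or more consecutive missed scheduled disease assessments, at the last evaluable disease assessment before them. It has no row for missed GVHD assessments.

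**SAP 7.7.** "There were no changes to the study conduct or planned analyses identified within the development of this SAP", relative to the protocol. SAP section 4 had promised that any change in methods from the protocol would be explained in the SAP.

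**The concern.** GRFS is a composite of qualifying GVHD, relapse and death. Every RFS event should therefore be a GRFS event in the same patient, on the same date or earlier if GVHD came first. That holds only if relapse and death follow the same missed-assessment rule in both endpoints.

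Under the SAP they do not. A relapse shown on an evaluable marrow, or a documented death, can leave GRFS because GVHD assessments were missing. A qualifying GVHD event can be lost in the same way. In addition, the rule cannot be programmed without a guess, because its trigger is undefined for GVHD assessments and those follow a different schedule. They also fall at Weeks 2 and 4, and under Table 1 of the protocol "SoC patients do not need to perform visit Weeks 2 or 4, unless clinically indicated".

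At stake is the meaning of a secondary endpoint that the protocol objectives say will be compared between arms. SAP 7.4.5 analyses it with the RFS methods, which include a hazard ratio and a stratified log-rank test. The same definition carries over to Subgroup D and to Group 2 patients in remission after bridging therapy.

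**Working it through.** The plan gives no figure to reproduce here. The check is to apply the three rules to the same patients.

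**Inputs.** The SAP 6.4.1.2 limits run from the last assessment before the event, with weeks counted from Day 0:

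- last assessment after the midpoint between randomization and Day 0, and up to Week 6: 24 + 2 = 26 weeks
- after Week 6, up to Week 18: 38 + 5 = 43 weeks
- after Week 18, up to Week 37: 78 + 5 = 83 weeks
- after Week 37, up to Week 78: 104 + 5 = 109 weeks

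**Assumption.** The same limits are borrowed for GVHD assessments, because the SAP gives none. Under Table 11, disease assessments before the last one shown are taken as done.

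| Case | Last disease assessment | Last GVHD assessment | Event | RFS (SAP) | GRFS (SAP) | GRFS (Table 11) |
|---|---|---|---|---|---|---|
| 1 | Week 24 | Week 4 | Relapse, Week 52 | 52 − 24 = 28, limit 83: event | 52 − 4 = 48, limit 26: censored at Week 4 | Event |
| 2 | Week 24 | Day 0 | Death, Week 30 | 30 − 24 = 6, limit 83: event | 30 − 0 = 30, limit 26: censored at Day 0 | Event |
| 3 | Day 0 | Week 24 | Death, Week 40 | 40 − 0 = 40, limit 26: censored at Day 0 | 40 − 24 = 16, limit 83: event | Censored at Day 0 (Weeks 12 and 24 missed) |

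Intervals of 1, 4 and 7 weeks from randomization to Day 0 give the same results.

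In cases 1 and 2 the SAP drops from GRFS an event that RFS and Table 11 both count. In case 3 it keeps an event that both would censor. With the trigger tied to disease assessments, RFS and GRFS agree in all three cases.

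**Size.** The documents give no rate of missed GVHD assessments. Purely as an illustration, if 2% to 10% of the 90 planned RFS events were affected, 0.02 × 90 = 1.8 to 0.10 × 90 = 9.0 events would leave GRFS. Case 3 works in the opposite direction and has no known rate either.

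**The case against.** **It is probably a drafting slip.** The censoring-date clause repeats itself, and elsewhere the word evaluable qualifies disease assessments, so one half was probably meant to say disease assessment. That is likely. But even that repair would leave the trigger tied to GVHD assessments, and the text as written is what would be programmed.

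**It will be rare.** GVHD and disease assessments share the Week 12, 24, 52 and yearly visits, and unscheduled visits follow the Week 24 assessments. A long gap in GVHD assessments alone needs repeated omission at shared visits. This stands, and it limits how often cases 1 and 2 would arise.

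**The endpoint is descriptive.** SAP 7.4.7.5 presents OS and GRFS in Group 1 for description only, with no multiplicity adjustment. This stands too, and keeps the point modest.

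**A stronger reading does not stand.** Because the Week 2 and 4 visits are required only in Arm A, a reader might infer that early events are lost there and MT-401 is favoured. At the planned MT-401 median of 8 + 6.5 = 14.5 months, the share of Arm A with an RFS event between Weeks 4 and 12 (0.92 and 2.76 months) is exp(−ln 2 × 0.92/14.5) − exp(−ln 2 × 2.76/14.5) = 0.957 − 0.876 = 0.081, or about 6 of 75. The documents do not support that inference:

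- It needs a rule of two missed GVHD visits, which neither document contains. Under the only limits the SAP defines, a patient last assessed at Day 0 with an event by Week 12 has a gap of at most 12 weeks against 26, and is not censored.
- The 6 are all expected events in that window, not those in patients who also missed both visits.
- Under those limits the extra visits slightly protect Arm A. A patient last assessed at Week 4 is censored only for events after Week 4 + 26 = 30; a patient last assessed at Day 0, for events after Week 26.
- Case 3 shows that the rule can also add events.

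**Conclusion.** The conflict is real and rests on the text alone: the SAP's GRFS gap rule and its censoring date differ from Protocol Table 11 and from the SAP's RFS rule, the gap is undefined for GVHD assessments, and SAP 7.7 declares no change. The event-free censoring date is a second undeclared difference.

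Relapses and deaths can therefore count for RFS and be censored in GRFS, and deaths can be censored in RFS and count in GRFS. The worked cases rest on borrowing the RFS limits. The number affected cannot be computed from the documents, and no direction of bias between arms is established.

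The effect is confined to GRFS, in Group 1 and in the Group 2 patients to whom the definition carries over. The primary RFS analysis and its type I error are untouched. This should be corrected, but it does not threaten the trial's main conclusion.

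**What to change.** 1. In the last sentence of the Group 1 GRFS definition in SAP 6.4.1.3, tie the gap rule and the censoring date for relapse and death to disease assessments, using the RFS limits in 6.4.1.2 and consistent with Table 11.
2. If a separate rule for GVHD events is wanted, define it for GVHD events only and declare it in 7.7. A gap in GVHD assessments would need its own limits and a statement of what happens to a later relapse or death. Counting every qualifying GVHD event at onset also departs from Table 11, whose missed-assessment row makes no exception for GVHD events.
3. For event-free patients, either restore the protocol's last evaluable disease assessment or declare the SAP's earlier-of-two-dates rule in 7.7.
4. Add a programming check that no RFS event is censored in GRFS.

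The cost is SAP wording and one derivation, with no new data. It is best settled before the SAP is finalized for the interim analysis.

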6.5 Data Quality Assurance

Report summaries will be generated using validated Base SAS® software, version 9.4 or higher, on a PC or server-based platform. Additional validated software may be used to generate analyses, as needed.

All SAS programs that create outputs or supporting analysis datasets will be validated by a second statistical programmer or biostatistician. At a minimum, validation of programs will consist of a review of the program log, review of output or dataset format and structure, and independent confirmatory programming to verify output results or dataset content. Additionally, all outputs will undergo a review by a senior level team member before finalization.

The content of the source data will be reviewed on an ongoing basis by project statistical programmers and statisticians. Data will be checked for missing values, invalid records, and extreme outliers through defensive programming applications, analysis-based edit checks, and other programmatic testing procedures. All findings will be forwarded to the project data manager for appropriate action and resolution.

7 STATISTICAL METHODS

7.1 General Methodology

Data will be analyzed by Precision for Medicine biostatistics personnel. Statistical analyses will be reported with tables, figures, and listings, presented in rich text format, and using recommended ICH numbering. Output specifications for all tables, figures, and listings will be in conformance with guidelines specified by the ICH in Appendix 7 of the *Electronic Common Technical Document Specification* (Apr 2003).

The primary analysis will include disease assessments associated with the first treatment regimen of MT-401 only. Re-treatment of MT-401 beyond planned study treatment (eg, re-starting MT-401 after relapse) will be considered as follow up anti-cancer therapy for the sake of efficacy analyses.

7.1.1 Reporting Conventions

Tables and figures will be summarized by study phase and cohort or treatment group. Tables summarizing demographics and other baseline characteristics will also include a column for all patients combined within study phase. Listings will be presented where appropriate and will be ordered by study phase, patient number, cohort or treatment group, and assessment or event date. For Cohort I-V and Group 2, the treatment group presented in tables, figures and listings will be based on the actual treatment received, unless otherwise noted. For Group 1, safety outputs will be based on the actual treatment received and other outputs will be based on the treatment a patient is randomized to.

In general, continuous variables will be summarized to indicate the study population sample size (N), number of patients with available data (n), mean, SD, median, 25th (Q1) and 75th (Q3)

quartiles, minimum, and maximum values. Categorical variables will be summarized by the population size (N), number of patients with available data (n), number of patients in each category, and the percentage of patients in each category. Unless otherwise noted, the denominator to determine the percentage of patients in each category will be based on the number of patients with available data. Select ordinal data may be summarized using both descriptive statistics and counts and percentages of patients in each category, as appropriate.

Non-zero percentages will be rounded to whole numbers. Rounding conventions for presentation of summary statistics will be based on the precision of the variable of summarization, as it is collected in its rawest form (ie, on the electronic case report form [eCRF] or as provided within an external file) and are outlined as follows:

- The mean and median will be rounded to one more decimal place than the precision of the variable of summarization, but no more than 2 decimal places;
- Measures of variability (eg, SD, SE) will be rounded to two more decimal places than the precision of the variable of summarization, but no more than 3 decimal places; and
- Minimum and maximum values will be presented using the same precision as the variable of summarization.

Other statistics (eg, CIs) will be presented using the same general rules outlined above, or assessed for the most appropriate presentation based on the underlying data.

Statistical significance testing will be two-sided and performed using $\alpha=0.05$. P-values will be reported for all statistical tests, rounded to four decimal places. P-values less than 0.0001 will be displayed as “<0.0001”; p-values greater than 0.9999 will be displayed as “>0.9999”.

7.1.2 *Summarization by Visit*

Data summarized by study visit will be based on the nominal, scheduled visit label as reported on the eCRF. Data collected at unscheduled visits will not be included in by-visit summaries, but will be considered when endpoint derivations potentially include multiple visits (eg, determination of baseline value, determination of worst post-baseline value, etc.). All data will be included in patient listings.

All efficacy data collected at unscheduled visits will be included in the derivation of efficacy endpoints.

7.1.3 *Data Handling Rules*

Unless otherwise noted, values reported as greater than or less than some quantifiable limit (eg, “< 1.0”) will be summarized with the sign suppressed in summary tables and figures, using the numeric value reported. Data will display on patient listings to include the sign.

7.1.4 **Standard Calculations**

Where appropriate, the calculated study day of each assessment or event will be presented with the assessment or event date on patient data listings, where study day will be determined as:

- The assessment/event date minus the date of first dose of MT-401 for patients enrolled in Cohorts I-V or Group 2
- The assessment/event date minus the date of randomization for all patients randomized in Group 1.

Other variables requiring calculations will be derived using the following formulas:

- **Days:** A duration between two dates expressed in days will be calculated as: later date – earlier date + 1
- **Months:** A duration expressed in months will be calculated by dividing the duration in days by (365.25 / 12);
- **Years:** A duration expressed in years will be calculated by dividing the duration in days by 365.25;
- **Change from Baseline:** Change from baseline will be calculated as the post-baseline value minus the baseline value;
- **Percentage Change from Baseline:** Percentage change from baseline will be calculated as the change from baseline divided by the baseline value, multiplied by 100.

7.1.5 **Definitions**

Standard definitions include:

- Actual follow-up time: last date known alive or death date – date of first dose of MT-401 (or date of randomization for Group 1 patient) + 1
- Baseline: the last available measurement prior to the first dose of MT-401 for patients enrolled in Cohorts I-V or Group 2. For patients randomized in Group 1, baseline for efficacy endpoints will be the last available measurement on or before the date of randomization. For patients randomized in Group 1, baseline for safety endpoints will be the last available measurement prior to the first dose of MT-401 for patients randomized to MT-401 and the last available measurement on or before the date of randomization for patients randomized to SOC.
- Potential follow-up time: data cutoff date – date of first dose of MT-401 (or date of randomization for Group 1 patients) + 1

- Study Day 0: the date of first dose of MT-401 (or date of randomization for Group 1 patients)
- Treatment emergent adverse events (TEAEs): Adverse events (AEs) with onset after the first dose of MT-401 or existing events that worsened after the first dose of MT-401 during the study. For the Group 1 SOC arm, TEAEs include AEs with onset after randomization or existing events that worsened after randomization.

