Study treatment is administered for all patients (except SoC - Group 1- Arm B) on Day 0 and every 2 weeks for a planned maximum of 3 doses. Patients randomized to SoC (Group 1B) at 80 days post-transplant may crossover to the relapse group (Group 2) if the patient is found to have relapse of disease (MRD* or frank relapse) and the subgroup is open and/or Sponsor agreement. After relapse and prior to bridging chemotherapy, the patient should perform assessments associated with the Screening visit if not already completed. The patient should perform the assessments associated with Baseline following bridging chemotherapy and prior to MT-401 administration. The patient will have their visits reset and have their MT-401 administered on Day 0 and follow the schedule of events from that point forward. Group 1- Arm B (SoC) patients will continue to follow the SoA minus administration of MT-401. Refer to Section 6 for additional dosing details. Administration of MT-401 can be delayed due to management of AEs or other toxicities, but patients should resume T cell infusions within 2 weeks of their scheduled dose. If greater than 2 weeks is needed, Sponsor will determine if patient can resume T cells infusions.

m All AEs and SAEs, from Day 0 and Baseline, respectively, to the Week 12 Visit will be collected; after Week 12, only treatment-related AEs and SAEs will be collected.

ⁿ Detailed studies outlined in Section 8.8.

o Additional details regarding the PRO questionnaire and associated instructions will be provided in a separate document.

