8.3.1. Period and Frequency for Collecting AE and SAE Information

All AEs will be collected from Day 0 until the Week 12 Visit at the time points specified in the SoA (Table 1), after which only treatment-related AEs and SAEs will be noted.

All SAEs from Baseline Visit to Week 12 Visit will be recorded and reported to the Sponsor or designee immediately and under no circumstance should this exceed 24 hours of learning of the event, as indicated in Appendix 1, Section 11.1. The investigator will submit any updated SAE data to the Sponsor within 24 hours of it being available. Additionally, any patient with any grade CRS or neurotoxicity will be reported in an expedited fashion within 24 hours of learning of event.

Investigators are not obligated to actively seek AEs or SAEs after conclusion of the study participation. However, if the investigator learns of any SAE, including a death, at any time after a patient has been discharged from the study, and he/she considers the event to be at least possibly related to the study intervention or study participation, the investigator must promptly notify the Sponsor.

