7.2 Analysis Populations

The analysis populations are defined as follows:

- All Treated Patients: Includes all patients who received at least one dose of MT-401 or were randomized to SOC.
- All Randomized Patients: Includes all patients in Group 1 who were randomized with final dose and manufacturing process and are MRD⁻ prior to randomization by central testing and local testing, if a local test was also performed. A patient randomized based on negative MRD result per central test but confirmed to be MRD⁺ will be excluded from Group 1 analysis.

When MRD testing occurs with different methodology (eg, flow cytometry and PCR), the patient is considered MRD⁺ if either test detects MRD. If adjudication occurs between central testing and local testing for the same type of testing (eg, flow by central testing and flow by local testing), the final adjudicated result will be taken into account for the confirmed MRD result. A patient confirmed to be MRD⁺ prior to randomization will be excluded from Group 1 and will be included in Group 2 analysis if treated with MT-401.

- Per-Protocol (PP) Population: Includes all treated patients, as defined above, who have no major protocol deviations. If there is <5% difference in the all randomized patient population and the PP population for Group 1, no analyses will be performed on the PP population.

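### Group 1 treatment-emergent events and the safety baseline start at first dose in the MT-401 arm but at randomization in SoC, and no rule closes the SoC window at crossover

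*SAP*

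**What the plan says.** **Start of the window.** SAP 7.1.5 defines treatment-emergent events generally as "Adverse events (AEs) with onset after the first dose of MT-401", or as existing events that worsen after it. For observation it adds: "For the Group 1 SOC arm, TEAEs include AEs with onset after randomization or existing events that worsened after randomization". Neither rule has an end date tied to Week 12, relapse or crossover.

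**Safety baseline.** In the same section, Arm A uses the last value before first dose. SoC uses "the last available measurement on or before the date of randomization for patients randomized to SOC".

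**Day 0.** The SAP has "Study Day 0: the date of first dose of MT-401 (or date of randomization for Group 1 patients". In the protocol (Section 1.3, footnote c), Day 0 is the first infusion, and the Sponsor schedules a Day 0 for every group, including the SoC arm. Footnote d adds: "Week 0 visit for SoC patients may occur between days 85-130 post-HSCT, as instructed by Sponsor".

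**Collection.** Protocol 8.3.1 states: "All AEs will be collected from Day 0 until the Week 12 Visit at the time points specified in the SoA". SAEs are recorded from the Baseline visit to Week 12. Footnote m of Section 1.3 adds: "after Week 12, only treatment-related AEs and SAEs will be collected".

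**Safety set.** The All Treated population in SAP 7.2 is defined as: "Includes all patients who received at least one dose of MT-401 or were randomized to SOC".

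**Crossover.** SoC patients who relapse may move to Group 2 and receive MT-401, with their visits reset to a new Day 0 (Protocol 1.3 and 6.3; SAP 6.3.2). SAP 7.1.1 bases Group 1 safety outputs on the treatment actually received. It does not say how to divide the events of a patient who was first observed and later dosed.

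**The concern.** Group 1 is the only randomized part of the trial, so it gives the only concurrent view of what happens to comparable patients without MT-401. Safety and tolerability is a stated Phase 2 secondary objective, and Protocol 9.3.5 presents safety by treatment arm. If the two columns of those tables count events over different periods, from different baselines and in differently selected patients, a difference between them may come from the definitions and not from the product. The open-ended SoC window adds a second problem: an event after a crossover dose of MT-401 still has its onset after randomization, so the SoC definition captures it.

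**Working it through.** The plan gives no figure for these windows, so there is none to reproduce. The check is to apply the SAP definitions to the protocol's collection rules.

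**1. An SAE between randomization and Day 0.** Protocol 8.3.1 records it in both arms, because SAE collection starts at Baseline. Under SAP 7.1.5 it is treatment-emergent in SoC, where onset follows randomization. In Arm A it is not, because onset precedes first dose. The same event is handled differently by arm.

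**2. Size of the SAE mismatch.**
- Arm A window: Day 0 to Week 12 = 12 × 7 = 84 days.
- SoC window: 84 + g days, where g is the time from randomization to Day 0.
- Ratio: (84 + g)/84.

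The gap g is an assumption. The pre-randomization disease assessment is at Day 80 ± 5 post-transplant and SoC Week 0 may fall on Days 85–130. An outer limit is therefore 130 − 75 = 55 days. The true maximum is shorter, because randomization must wait for the central MRD result.

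The last column shows what SoC would report at equal true risk, if Arm A has a 20% 84-day incidence (assumed) and the event rate is constant: 1 − 0.8^ratio.

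| g (days) | SoC window (days) | Ratio | SoC incidence shown |
|---|---|---|---|
| 15 | 99 | 1.18 | 23% |
| 30 | 114 | 1.36 | 26% |
| 45 | 129 | 1.54 | 29% |
| 55 (outer limit) | 139 | 1.65 | 31% |

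**3. Non-serious events.** Under the protocol's Day 0, these are collected from the scheduled Day 0 in both arms. Gap events are then recorded in neither arm, and new events share one onset window. The SoC definition simply reaches back over a period with no data. If the SAP's Day 0 (randomization) were taken to govern collection, the mismatch in step 2 would extend to all adverse events. The documents leave both readings open.

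**4. Baselines.** Laboratory grade shifts (SAP 7.5.4) and chronic GVHD shifts (SAP 7.5.5.3) are measured from baseline. A change that arises in the gap can be part of the Arm A baseline but a post-baseline shift in SoC. SAP 7.5 also sets the by-visit safety baseline before first study drug, which a SoC patient does not have.

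**5. Who is in the table.** A patient who dies or withdraws between randomization and Day 0 stays in the SoC safety set. The same patient in Arm A, never dosed, is not in the set.

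**6. Crossover.** By the literal definition, an MT-401 event in a crossover patient is an SoC treatment-emergent event and may also be reported under Group 2. The documents do not give the number of crossovers, so this is illustration only. Let p be the true SoC incidence, c the share crossing over and q their chance of an event on MT-401, taken as independent. The counted incidence is 1 − (1 − p)(1 − cq).
- p = 30%, c = 25%, q = 20%: 1 − 0.70 × 0.95 = 33.5%.
- p = 30%, c = 50%, q = 30%: 1 − 0.70 × 0.85 = 40.5%.

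**The case against.** The strongest reply has four parts.

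**The stakes are limited.** SoC safety data are shown for reference (Protocol Table 8), the summaries are descriptive, and no test, primary endpoint or stated stopping rule uses them. This stands, and it is why the point is a should-fix. A reader might infer that the tables cannot be interpreted at all. The text does not support that: under the protocol's Day 0, new non-serious events share one onset window.

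**Crossover may already be handled.** The treatment-actually-received rule in SAP 7.1.1, the visit reset, and the new consent and eligibility check (Protocol 10.2) can be read as sending post-crossover events to Group 2. That is a fair reading, so double counting is possible, not certain. But no sentence says so, and the SoC definition literally includes these events.

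**Some alignment exists.** SAP 7.5.2 allows a Group 1 summary from randomization, and the 30- and 60-day death summary shifts the SoC clock (SAP 7.5.3). The first is optional and does not address crossover. The second covers deaths only. Neither changes the main event, SAE or shift tables.

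**Size and direction are easy to overstate.** A reader might use the 8-month SoC median RFS to gauge SAE inflation, or the expected SoC share of the 90 RFS events to gauge crossover exposure. Neither works. RFS events include molecular relapse, and Protocol 8.3 does not treat death from progression or hospitalization for signs of the disease as adverse events. Crossover also needs an open subgroup and/or Sponsor agreement. A reader might also infer that late events can appear only in Arm A, since observation has no treatment-related events. The footnote's wording does not settle whether the treatment-related limit after Week 12 applies to SAEs as well as AEs.

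A further objection is that starting at Day 0 excludes patients after randomization. It does, so a randomization-onward table must accompany it.

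**Conclusion.** The point holds, as a should-fix. By the SAP's own definitions, the arm-by-arm Group 1 safety tables are not like-for-like in three respects: the SAE window, the baseline for shifts and worsening, and entry to the safety set. A fourth, the treatment of events after crossover dosing, is left unstated.

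The SAE window in SoC is 1.18 to 1.54 times that in Arm A for assumed gaps of 15 to 45 days. This rests on an 84-day Arm A window and on the protocol's Day 0; the documents do not fix the gap. Non-serious events are affected only if the SAP's Day 0 governs collection.

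A reader might infer that the definitions make MT-401 look safer. The longer SAE window and any counted crossover events do push that way. Late treatment-related events in Arm A could push the other way, and neither the crossover count nor the late-collection rule is settled. The net direction is unknown.

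**What to change.** Amend SAP 7.1.5, with matching edits in SAP 7.5:

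- **(a)** Reconcile the SAP and protocol definitions of Day 0 for Group 1.
- **(b)** For the main Group 1 tables, use the same start and safety baseline in both arms, running through Week 12. The start is the scheduled Day 0 or, where there is no such visit, the artificial Day 0 that SAP 6.4.1.2 already derives for RFS.
- **(c)** End the SoC window at the first MT-401 dose after crossover, and report later events under Group 2 only.
- **(d)** Make a randomization-onward summary of SAEs and deaths mandatory, for all randomized patients by assigned arm, with the same crossover cut-off.
- **(e)** Show treatment-related events after Week 12 separately from the between-arm tables.

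Under (b) both windows are 84 days (ratio 1.00), and under (c) no event after a crossover dose falls in the SoC column. The cost is SAP wording and one extra table, using data already collected. The drawback is that the Day 0 table omits patients lost before Day 0; (d) covers them for SAEs and deaths. The change should be made before safety is analyzed by arm, including for the DMC interim review.
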